9.6 Pregnancy reporting

All pre-menopausal women who are not surgically sterile will have a urine pregnancy test. A positive urine pregnancy test requires immediate interruption of study drug until serum β -hCG is performed and found to be negative.

To ensure subject safety, each pregnancy occurring after signing the informed consent must be **reported to Novartis within 24 hours** of learning of its occurrence. The pregnancy should be followed up to determine outcome, including spontaneous or voluntary termination, details of the birth, and the presence or absence of any birth defects, congenital abnormalities, or maternal and/or newborn complications.

Pregnancy must be recorded on the Pharmacovigilance Pregnancy Form and reported by the investigator to the local Novartis Chief Medical Office and Patient Safety (CMO & PS) Department. Pregnancy follow-up should be recorded on the same form and should include an assessment of the possible relationship to the study treatment.

Any SAE experienced during the pregnancy and unrelated to the pregnancy must be reported on a SAE form.

The study drug must be discontinued*, though the subject may stay in the study, if she wishes to do so. All assessments that are considered as a risk during pregnancy must not be performed. The subject may continue all other protocol assessments.

Pregnancy outcomes should be collected for the female partners of any males who took study treatment in this study. Consent to report information regarding these pregnancy outcomes should be obtained from the mother.

10 Data review and database management

10.1 Site monitoring

Before study initiation, at a site initiation visit or at an investigator's meeting, a Novartis representative will review the protocol and data capture requirements (eCRF) with the investigators and their staff. During the study Novartis employs several methods of ensuring protocol and GCP compliance and the quality/integrity of the sites' data. The monitor will visit the site to check the completeness of subject records, the accuracy of data capture / data entry, the adherence to the protocol and to Good Clinical Practice, the progress of enrollment, and ensure that study drug is being stored, dispensed, and accounted for according to specifications. Key study personnel must be available to assist the monitor during these visits.

Continuous remote monitoring of each site's data may be performed by Novartis or CRO working on behalf of Novartis. Additionally, a central analytics organization may analyze data and identify risks & trends for site operational parameters, and provide reports to Novartis Clinical Teams to assist with trial oversight.

The investigator must maintain source documents for each subject in the study, consisting of case and visit notes (hospital or clinic medical records) containing demographic and medical information, laboratory data, electrocardiograms, and the results of any other tests or assessments. All information on CRFs must be traceable to these source documents in the subject's file. The investigator must also keep the original informed consent form signed by the subject (a signed copy is given to the subject).

The investigator must give the monitor access to all relevant source documents to confirm their consistency with the data capture and/or data entry. Novartis monitoring standards require full verification for the presence of informed consent, adherence to the inclusion/exclusion criteria, documentation of SAEs, and the recording of data that will be used for all primary and safety variables. Additional checks of the consistency of the source data with the CRFs are performed according to the study-specific monitoring plan. No information in source documents about the identity of the subjects will be disclosed.

10.2 Data collection

Designated investigator staff will enter the data required by the protocol into the Electronic Case Report Forms using fully validated software that conforms to 21 CFR Part 11 requirements. Designated investigator site staff will not be given access to the EDC system until they have been trained. Automatic validation programs check for data discrepancies and, by generating appropriate error messages, allow the data to be confirmed or corrected before transfer of the data to the CRO working on behalf of Novartis. The Investigator must certify that the data entered into the Electronic Case Report Forms are complete and accurate. After database lock, the investigator will receive copies of the subject data for archiving at the investigational site.

Data not requiring a separate written record will be defined in the Site Operations Manual and **Assessment schedule** (Section 8.1) and can be recorded directly on the CRFs. All other data captured for this study will have an external originating source (either written or electronic) with the CRF not being considered as source.

All data should be recorded, handled and stored in a way that allows its accurate reporting, interpretation and verification.

10.3 Database management and quality control

Novartis staff and CRO working on behalf of Novartis review the data entered into the CRFs by investigational staff for completeness and accuracy and instruct the site personnel to make any required corrections or additions. Queries are sent to the investigational site using an electronic data query. Designated investigator site staff is required to respond to the query and confirm or correct the data. If the electronic query system is not used, a paper Data Query Form will be faxed to the site. Site personnel will complete and sign the faxed copy and fax it back to CRO working on behalf of Novartis who will make the correction to the database. The signed copy of the Data Query Form is kept at the investigator site.

Concomitant medications entered into the database will be coded using the WHO Drug Reference List, which employs the Anatomical Therapeutic Chemical classification system. Medical history/current medical conditions and adverse events will be coded using the Medical dictionary for regulatory activities (MedDRA) terminology.

Laboratory samples will be processed centrally and the results will be sent electronically to Novartis (or a designated CRO).

Details regarding patient diary, PRO, and CRO data collection will be provided in SOM.

At the conclusion of the study, the occurrence of any emergency code breaks will be determined after return of all code break reports and unused drug supplies to Novartis.

The occurrence of relevant protocol deviations will be determined. After these actions have been completed and the database has been declared to be complete and accurate, it will be locked and the treatment codes will be unblinded and made available for data analysis. Any changes to the database after that time can only be made after written agreement by Novartis management.

Commercially Confidential Information

10.4 Data Monitoring Committee

Not required.

10.5 Adjudication committee

Not required.

11 Data analysis

The analysis will be conducted on all subject data at the time the trial ends. Any data analysis carried out independently by the investigator should be submitted to Novartis before publication or presentation.

11.1 Analysis sets

For all analysis sets, subjects will be analyzed according to the study treatment(s) received.

The safety analysis set will include all subjects that received any study drug.

The PK analysis set will include all subjects with at least one available valid (i.e. not flagged for exclusion) PK concentration measurement, who received any study drug and with no protocol deviations that impact on PK data.

The PD analysis set will include all subjects with available PD data and no protocol deviations with relevant impact on PD data.

11.2 Subject demographics and other baseline characteristics

All data for background and demographic variables will be listed by treatment group and subject. Summary statistics will be provided by treatment group.

Relevant medical history, current medical conditions, results of laboratory screens, drug tests and any other relevant information will be listed by treatment group and subject.

11.3 Treatments

Data for study drug administration (rescue medication) and concomitant therapies will be listed by treatment group and subject.

11.4 Analysis of the primary variable(s)

The primary aim of this study is to assess the efficacy of secukinumab 300 mg s.c. vs. placebo in patients with overuse rotator cuff tendinopathy in relieving clinical symptoms at week 14

11.4.1 Primary Variable(s)

The primary variable, the WORC score, will be available at Baseline and weeks 2, 4, 8, 12 and 14

11.4.2 Statistical model, hypothesis, and method of analysis

The primary end-point (change from baseline in WORC score at Week 14) will be analyzed by repeated measures analysis of covariance including all WORC scores available. Change at Week 14 will be compared between treatments to address the primary objective. The baseline WORC score will be included as a covariate. The stratification factors partial tear/no tear and previous steroid injection (yes/no) will be included in the model as fixed effects. A 95% one-sided (90% two-sided) confidence interval for the treatment effect at Week 14 will be reported. Missing variables will be considered missing at random.

Initially, models with an unstructured within-subject covariance and a separate mean for each treatment and time point will be fitted. These models may be reduced in number of covariance and mean parameters by model comparison using tools such as the BIC criterion for model fit.

11.4.3 Handling of missing values/censoring/discontinuations

Commercially Confidential Information

11.4.4 Summary statistics of safety

Vital signs

All vital signs data will be listed by treatment group, subject, and visit/time and if ranges are available abnormalities (and relevant orthostatic changes) will be flagged. Summary statistics will be provided by treatment and visit/time.

Clinical laboratory evaluations

All laboratory data will be listed by treatment group, subject, and visit/time and if normal ranges are available abnormalities will be flagged. Summary statistics will be provided by treatment and visit/time.

Adverse events

All information obtained on adverse events will be displayed by treatment group and subject.

The number and percentage of subjects with adverse events will be tabulated by body system and preferred term with a breakdown by treatment. A subject with multiple adverse events within a body system is only counted once towards the total of this body system.

11.4.5 Sensitivity analyses

Not applicable.

11.5 Analysis of secondary variable(s)

Secondary variables include:

- Change from baseline in WORC score at weeks 2, 4, 8, 12, 18 and 24
- Disability of Arm, Shoulder and Hand Questionnaire (QuickDASH) score at weeks 2, 4, 8, 12, 14, 18 and 24
- American Shoulder and Elbow Surgeons Shoulder Evaluation Form(ASES) score at weeks 2, 4, 8, 12, 14, 18 and 24
- EQ5D score at weeks 2, 4, 8, 12, 14, 18 and 24
- Pain score using a VAS scale (considering the last 24 hours) at weeks 2, 4, 8, 12, 14, 18 and 24
- Patient global assessment (PGA) score using a VAS scale (considering the last 24 hours), at weeks 2, 4, 8, 12, 14, 18 and 24
- Physician global assessment (PhGA) score using a VAS scale (considering the last 24 hours), at weeks 2, 4, 8, 12, 14, 18 and 24
- MRI Sein score at weeks 8, 14 and 24

Secondary variables (except Sein score) will be summarized descriptively and analyses similar to the primary analysis will be performed.

The secondary endpoint (Sein MRI score at week 14) will be analyzed by ordinal categorical regression. A model with an additive treatment effect on the cumulative logistic scale will be used, and the common treatment effect estimated and reported together with 90% asymptotic two-sided confidence intervals. Baseline SEIN score will be included as a covariate and the stratification factors, partial tear/no tear and previous steroid injection (yes/no) will be included in the model as fixed effects.

11.5.1 Efficacy / Pharmacodynamics

Not Applicable

11.5.2 Safety

Vital signs

All vital signs data will be listed by treatment group, subject, and visit/time and if ranges are available abnormalities (and relevant orthostatic changes) will be flagged. Summary statistics will be provided by treatment and visit/time.

Clinical laboratory evaluations

All laboratory data will be listed by treatment group, subject, and visit/time and if normal ranges are available abnormalities will be flagged. Summary statistics will be provided by treatment and visit/time.

Adverse events

All information obtained on adverse events will be displayed by treatment group and subject.

The number and percentage of subjects with adverse events will be tabulated by body system and preferred term with a breakdown by treatment. A subject with multiple adverse events within a body system is only counted once towards the total of this body system.

11.5.3 Pharmacokinetics

Commercially Confidential Information

11.5.4 Pharmacokinetic / pharmacodynamic correlation analysis

Not Applicable.

11.5.5 Other assessments

Immunogenicity

All immunogenicity results will be listed by treatment group, subject and visit/time.

11.6 Analysis of exploratory variables

The statistical analysis for exploratory variables will be described in the RAP.

Commercially Confidential Information

11.7 Sample size calculation

From ([de Witte et al 2012](#)), one can infer an SD of change in the WORC score from baseline to 6 weeks of approximately 22 percentage points. By conservatively assuming a linear increase in the change score variability, the 14 week SD would be 22 multiplied by the square root of 1.53 (14/6); that is, 34 percentage points.

Assuming a clinically meaningful difference of 20 percentage points results in an effect size of $20/34=0.59$. With this effect size, 40 subjects per group completing week 14 will provide power exceeding 80% to detect a significant difference between treatments by one-sided test at significance level 0.05.

11.8 Power for analysis of key secondary variables

To address the secondary MRI endpoint (Sein score at Week 14), the sample size of 40 subjects per group completing Week 14 will also provide approximately 80% power to detect an odds ratio at or above 50%, i.e., that the odds of a Sein score improvement is at least 50% higher in the treated group than in the placebo group, again by one-sided test at nominal significance level 0.05. This assumes a proportional cumulative odds model as described in ([Whitehead 1993](#)).

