6.2 Treatment arms

Patients will be assigned to one of the following 2 treatment arms in a 1:1 ratio, with approximately 50 patients per arm.

- Group 1: Secukinumab 300 mg s.c. (2 x 150 mg)
- Group 2: Placebo s.c. (2 injections)

Treatment is administered at Day 1 (randomization visit), and Weeks 1, 2, 3, 4, 8 and 12.

Subjects who complete the assessments associated with Week 14 visit should continue the study in a (treatment free) follow up period of 10 weeks up to 24 weeks.

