8.6.3.1 MRI of the shoulder, Sein score and Bauer score

The MRI Sein score will be used primarily to grade supraspinatus tendinosis at screening using a modified 4-point scale ([Sein et al 2007](#)), and monitor changes in this grading over time as a treatment outcome (secondary objective). Tendinopathy will be characterized by thickened inhomogeneous rotator cuff tendon with increased signal intensity on all pulse MRI sequences, yet not as bright as the fluid on typical T2-weighted images. Since tendonitis and partial thickness cuff injuries are prevalent in sporting activity and in middle age, another grading system, the Bauer score, will be used as an exploratory endpoint for a differentiated assessment of supraspinatus partial tears and tendonitis ([Bauer et al 2014](#)). A 9-point tendinopathy grade will be generated out of this approach, including sub-scores for tendonitis (0-2), tear thickness (0-4) and AP tear size (0-3). Finally these images will also be used to measure thickness of the rotator cuff tendon and assess for presence of bursitis in the area of the rotator cuff.

Enhancement of the subacromial bursa will be assessed. Images will be scored on a scale of 0–2 depending on the maximum thickness of enhancing tissue: 0: no abnormal enhancement; 1: up to 3 mm thickness of enhancing tissue; 2: 3 mm or more enhancing tissue ([Hodgson et al 2012](#)).

Commercially Confidential Information

MR images will be acquired at 3T in multiple planes by using an imaging sequences optimized for tendon/surrounding tissue separation and adapted to the MRI system capabilities. All MRI scans will be sent for central reading and all results obtained post Baseline visit will remain blinded to the investigator, patient and sponsor until after the primary endpoint analysis at week 14. Detailed information can be located in the imaging manual. The coded MRI medical images will be used primarily for analysis as described in this protocol; however, the images may also be used for the development and evaluation of new analysis methods directly related to the area of research that this study covers.

Commercially Confidential Information

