6.2.4 Statistical model, assumptions and hypotheses

The secondary variables (except for the Sein score) will be summarized descriptively and analyzed similar to the primary analysis.

The secondary variable Sein MRI score at weeks 14 and 24 will be analyzed by ordinal categorical regression. A model with an additive treatment effect on the cumulative logistic scale will be used, and the common treatment effect estimated and reported together with 90% asymptotic two-sided confidence intervals. Baseline SEIN score will be included as a covariate and the stratification factors, partial tear/no tear and previous steroid injection (yes/no) will be included in the model as fixed effects.

All the secondary analyses will also be repeated for patients where the affected arm is the dominant arm.

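### Protocol 11.8 claims about 80% power for an odds ratio of 1.5 on the Sein score with 40 per group; the unadjusted proportional-odds test it describes has at most about 27%

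*Protocol*

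**What the plan says.** Protocol 11.8 bases the secondary MRI power on "the sample size of 40 subjects per group completing Week 14" and states that this "will also provide approximately 80% power to detect an odds ratio at or above 50" per cent. The same sentence defines the effect: "the odds of a Sein score improvement is at least 50% higher in the treated group than in the placebo group". The test is set "again by one-sided test at nominal significance level 0.05", under a proportional cumulative odds model. No distribution of Sein grades is given.

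Related passages:

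- Protocol 8.6.3.1: the Sein score is used to "grade supraspinatus tendinosis at screening using a modified 4-point scale" and to follow change over time.
- Protocol 6.2: patients are assigned "in a 1:1 ratio, with approximately 50 patients per arm".
- Protocol 11.5: the analysis is a cumulative logit model. "Baseline SEIN score will be included as a covariate and the stratification factors" are fixed effects in the same model.
- SAP 6.2.4: the same model, with "the common treatment effect estimated and reported together with 90% asymptotic two-sided confidence intervals". The SAP text available neither repeats nor corrects the power figure.

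**The concern.** An odds ratio of 1.5 is a modest shift on an ordinal scale, and 80 patients carry little information about it. The primary calculation in 11.7 relies on a standardised difference of 0.59 to pass 80% with the same 40 per group. It would be surprising if a four-grade MRI score reached similar power for a much smaller effect.

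What is at stake is how the Sein result is read. Sein is the structural endpoint, 11.8 places it under key secondary variables, and Protocol 1.1 says the data are meant to support Phase III planning. A reader who believes the 80% would expect to miss a true odds ratio of 1.5 about one time in five, and would treat a non-significant result as fairly strong evidence against it. If power is near 26%, such an effect is missed about three times in four.

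**Working it through.** **Inputs.** 40 completers per group, so N = 80 (11.8); 1:1 allocation (6.2); odds ratio 1.5, ln 1.5 = 0.4055 (11.8); one-sided 0.05, z = 1.645 (11.8); four grades (8.6.3.1). Grade proportions are not given, so I use a bound that needs none and some assumed cases.

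**Formula.** For the unadjusted proportional-odds score test with 1:1 allocation:

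- V = (N/12) × (1 − Σp³), where p are the grade proportions averaged over the two arms
- power = Φ(ln OR × √V − 1.645)

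**Trying to reproduce 80%.** Since 1 − Σp³ cannot exceed 1, V is at most 80/12 = 6.667. Then 0.4055 × √6.667 = 1.047, 1.047 − 1.645 = −0.598, and Φ(−0.598) = 27.5%. A finite-sample form of V gives 27.1%. For 80% power, V would have to be (1.645 + 0.842)²/0.4055² = 37.6, more than five times the maximum available.

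**Assumed grade distributions, 40 per group:**

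| Average proportions | V | Power, OR 1.5 | Power, OR 2 | OR for 80% |
|---|---|---|---|---|
| Bound, any distribution | 6.67 | 27.5% | 55.8% | 2.62 |
| Four equal grades | 6.25 | 26.4% | 53.5% | 2.70 |
| .02, .49, .47, .02 | 5.19 | 23.5% | 47.4% | 2.98 |
| .05, .80, .10, .05 | 3.245 | 18.0% | 34.6% | 3.98 |

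Σp³ is smallest when the grades are equally filled, so the second row is the best case for exactly four grades. The first row also covers an outcome with more categories.

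**Simulation (40,000 trials per case).** Two separate runs with four equal grades gave 25.9% and 26.9% at OR 1.5, and 78.4% and 78.7% at OR 2.7. Twenty equal categories gave 27.3% at OR 1.5. The two concentrated cases gave 23.9% and 17.9% at OR 1.5.

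**Completers needed at OR 1.5.** n per group = 6 × (1.645 + 0.842)²/(0.4055² × (1 − Σp³)): at least 226, or 241 with four equal grades.

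**Other readings of the sentence:**

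- All 50 per arm complete: at most 31.8%.
- 80 per group instead of 80 in total: at most 43.5%.
- Two-sided 0.05: 17 to 18% (four equal grades and the bound).
- Odds doubled or halved: at most 55.8%.
- Log odds ratio of 0.5: about 35% with four equal grades.
- Improvement as a binary outcome: at most about 23%.
- Risk ratio of 1.5: 75% at a placebo improvement rate of 0.5, 94% at 0.6.
- A difference of 50 percentage points: above 99% at the placebo rates tried (0.1 to 0.3).

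The last two can pass 80%, but 11.8 speaks of odds and a proportional-odds model, so neither is what it states.

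**Covariate adjustment.** The planned model adjusts for baseline Sein score and two strata. Using expected information and assuming baseline grades I to III at .3/.4/.3, two binary strata and four equal Week 14 grades:

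- If 1.5 is the adjusted odds ratio, power is 26.2%, 24.2%, 21.2% and 19.5% at latent baseline-to-Week 14 correlations of 0, 0.65, 0.86 and 0.93. Small simulations with baseline grade as the only covariate gave about 23 to 30%, with Monte Carlo error of 1 to 2 points.
- If 1.5 is the unadjusted odds ratio, adjusted-test power is 29.8%, 38.6%, 50.4%, 62.6% and 78.6% at correlations of 0.39, 0.65, 0.79, 0.86 and 0.93.

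**Meaning for the result.** With four equal grades, significance needs an observed odds ratio of exp(1.645/√6.25) = 1.93. An observed 1.5 would have a 90% interval of 1.5/1.93 to 1.5 × 1.93, that is, 0.78 to 2.90.

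**Contrast.** The primary claim in 11.7 does reproduce: a difference of 20 with SD 34 and 40 per group, one-sided 0.05, gives 83.8%, in line with more than 80%. The problem is confined to 11.8.

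**The case against.** The arithmetic cannot be rescued by the missing grade distribution, because the ceiling does not depend on it. The serious objections concern weight and detail.

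- **Little follows from it.** The test is at a nominal level, the trial is sized on WORC, and Sein stands among eight unranked secondary variables with no hierarchy. The word key appears only in the 11.8 heading. The planned 90% interval will show the imprecision anyway. This stands, and it limits the consequence. It does not make the sentence correct.
- **Which number is wrong is unknown.** The documents show that 50% and 80% are incompatible, not which one was miscalculated or mistyped. This stands too. The correction should therefore give both the power at 1.5 and the odds ratio at which 80% holds.
- **Adjustment could help.** With an unadjusted odds ratio of 1.5 and a latent correlation of 0.93, power comes to 78.6%. That is a real exception, but the documents state no such correlation, and 11.8 claims no gain from covariates. The adjusted figures also rest on assumed inputs.
- **The concentrated cases depend on convention.** If .05/.80/.10/.05 is the placebo distribution and the effect runs towards higher categories, simulation gives 71% at an odds ratio of 3 and 88% at 4. If it is the pooled distribution, simulation gives 76.8% at 4. Across conventions the odds ratio for 80% lies between about 3 and slightly above 4, so these values are illustrations. The distribution-free bounds are firm.

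**Conclusion.** The power statement in 11.8 is wrong as written. For the effect, sample size, test and model that it names, unadjusted power is at most 27.5%, against about 80% stated: roughly a threefold overstatement. That bound rests only on 1:1 allocation, 80 completers, a one-sided 0.05 level and the proportional-odds information formula. The figures of 26% (four equal grades) and 18 to 23.5% (concentrated grades) rest on assumed distributions. No reading that keeps to an odds ratio brings the unadjusted test to 80%; the most generous, an odds ratio of 2 or 0.5, gives at most 56%. Adjustment rescues the claim only if 1.5 is an unadjusted odds ratio and the latent correlation is above about 0.9, which the documents do not support.

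The consequence is limited to the planning and reading of one secondary endpoint. The primary power, the sample size and every planned analysis are unaffected. The statement should be fixed.

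**What to change.** Replace the power statement in Protocol 11.8 with wording such as:

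> With 40 completers per group (one-sided nominal 0.05, unadjusted proportional-odds test), power for an odds ratio of 1.5 is at most about 27%: about 26% if the four Sein grades are equally filled, and about 18 to 23% if most patients fall in one or two grades. About 80% power is available only for an odds ratio of at least about 2.6 (about 2.7 with four equal grades, about 3 to 4 with concentrated distributions). Adjustment for baseline Sein score and strata is not expected to close this gap. A non-significant result does not exclude an odds ratio of 1.5 and is to be read with the planned 90% confidence interval.

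If the sponsor has an expected Week 14 Sein distribution, state it and give the power for that case. If a different odds ratio was intended, state it with its own power. The sentence on adjustment is a judgement based on assumed correlations; it can be replaced by the sponsor's own calculation or left out, provided the bounds stay.

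The cost is a wording change in one section and a less favourable power figure. The sample size, the Sein model and the power in 11.7 do not change.
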